Oxytocin is a neuropeptide known to have prominent anxiolytic and prosocial effects. Among both animals and humans, oxytocin is known to mitigate the effects of social stress on addictive behaviors. Among normative couples, preliminary data suggests that oxytocin promotes more positive conflict resolution skills. Taken together, this literature suggests that oxytocin holds promise as a tool to modulate the effects of dyadic conflict on addictive behaviors. If evidence supporting this notion emerged, these data would support the investigation of oxytocin as a potential augmenter to couples therapies for substance abuse problems. However, the first step toward evaluating oxytocin in this role, and the primary objective of the proposed study, is to examine the extent to which oxytocin improves conflict resolution skills among couples with substance abuse. Our secondary objective is to examine the extent to which oxytocin mitigates couples' subjective, physiological, and neuroendocrine reactivity to dyadic conflict. Thirty-six couples (n=72) consisting of at least one partner with recent substance abuse will participate in the study. The study will consist of one 4-hour laboratory visit. Couples will complete a thorough psychosocial assessment interview and two 10-minute videotaped conflict resolution tasks using a well-established paradigm. Participants will be randomly assigned to self-administer either a 40 IU dose of intranasal oxytocin or placebo. We will implement a double-blind design. We will examine standardized, repeated dependent measures of change in each partner's conflict resolution skills, subjective, physiological, and neuroendocrine responses to the conflict resolution task. The following specific aims are proposed:

Specific Aim 1: Examine the effects of oxytocin on couples' conflict resolution skills.

Couples will complete a psychosocial assessment and two 10-minute videotaped conflict resolution tasks. 45 minutes prior to the second conflict resolution task, a 40-IU dose of intranasal oxytocin or saline spray will be administered to both partners. Conflict resolution skills will be coded according to a well-established system and compared from Task 1 to Task 2.

Specific Aim 2: Examine the effects of oxytocin on couples' subjective, physiological, and neuroendocrine reactivity to the conflict resolution task.

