The proposed study targets a population facing considerable challenges that may influence the research team's ability to recruit participants through the duration of the study. The PI will recruit adequate research staff to assist in the recruitment, assessment, and scheduling appointments. All study staff will be trained in available techniques that the PI and [name] have used in previous studies to minimize participant burden and facilitate participants' access to study staff and their attendance at study appointments. Study staff will provide appointment reminder cards, will call or text the day prior to each appointment to remind participants of study appointments, and will contact participants immediately by phone and/or email if appointments are missed.

G. Data Analysis

General. Data analysis will be conducted using SPSS v. 21 and Mplus™ software version 5.2 or higher (57). All analyses will be tested using significance level <0.05. Preliminary analyses will include determining the characteristics of the sample including demographic variables and descriptive statistics for all variables of interest included in the study. Reliability of assessment measures will be calculated prior to beginning main study analyses. We will also compare individuals who were eligible but declined

participation following screening and/or informed consent with those who chose to participate. We will also compare participants who withdrew or dropped out of the study following baseline assessment with study completers on demographic variables and main variables of interest. Subsequent analyses will be theory-driven and informed by the primary research questions of this study. Bivariate associations between variables will be examined via correlation. Demographic variables with significant bivariate associations with main outcome variables will be employed as covariates in subsequent analyses. The PI will conduct these preliminary analyses in consultation with [name] and biostatistics consultation provided through SCTR at MUSC.

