Missing Data. Given the multi-modal assessment strategy employed in the proposed study, it is expected that only a small proportion of missing data will appear. However, in the event that more than 10% of data on a key variable is missing, we will attempt to reduce bias and maximise statistical power by choosing and employing a method for imputing data. This method will be chosen in collaboration with [name] and biostatistics consultation available through SCTR resources.

Preliminary Analysis. All study variables will be examined to assess normality, distributions, and outliers. Non-normal data will be transformed using log-10 or natural log transformation in an attempt to achieve greater normality of distributions. If appropriate normality cannot be achieved on key variables of interest, non-parametric statistical analyses will be employed.

Longitudinal Analysis. Linear regression analyses, structural equation modeling, and hierarchical linear modeling (HLM) will be employed to test study hypotheses. These approaches, HLM in particular, are ideally suited to analyze non-independent data reported by dyads (58). Multilevel models will be estimated, where the statistical non-independence of each partner's data is controlled by estimating each partner's parameters simultaneously through a procedure described in greater detail by Raudenbush and colleagues (59).

Hypothesis 1: Couples will demonstrate improved conflict resolution skills from the first observational conflict resolution task to the second following the administration of oxytocin.

Hypothesis 2: Couples will demonstrate lessened subjective, physiological, and neuroendocrine reactivity to the second conflict resolution task following the administration of oxytocin.

First, average levels of each of the outcome variables will be estimated through the use of a level-1 equation of a multilevel model. This approach will allow us to examine the average estimates of change in each of the outcome variables over the multiple time points assessed. Chi-square analyses and effect sizes will also be estimated to examine the between-subjects variance in each variable of interest. Chi-square analyses will indicate whether changes on each variable differed significantly across either or both partners. We will also examine the within-subject relationships between mental health and substance abuse variables over time for both partners.

H. Strengths of the Research Design

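### No oxytocin-versus-placebo contrast is written for any outcome, and the protocol contradicts itself on whether a placebo arm exists

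*Combined protocol and SAP*

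**What the plan says.** **The design.** Section 1 states "Participants will be randomly assigned to self-administer either a 40 IU dose of intranasal oxytocin or placebo" and "We will implement a double-blind design". Section 4.D agrees: the procedures text and the 9:50 row of the Laboratory Task Timeline have couples take one spray or the other, and the oxytocin administration paragraph speaks of participants assigned to an oxytocin condition. In section 6, the adverse event definition refers to randomised subjects.

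Other places differ. Section 4.I lists the absence of a control group as a limitation and says that a more rigorous design might include a placebo group. Section 4.A says that both partners receive oxytocin, and the payment text in section 4.E refers only to the oxytocin dose.

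**The analysis.** Aim 1: "Conflict resolution skills will be coded according to a well-established system and compared from Task 1 to Task 2". In section 4.G, the first hypothesis is that "Couples will demonstrate improved conflict resolution skills from the first observational conflict resolution task to the second following the administration of oxytocin". It does not mention placebo. The second, on reactivity, names no comparator either; it is that "Couples will demonstrate lessened subjective, physiological, and neuroendocrine reactivity to the second conflict resolution task following the administration of oxytocin". Of the multilevel model, section 4.G says "This approach will allow us to examine the average estimates of change in each of the outcome variables over the multiple time points assessed". Its chi-square tests examine between-subjects variance, and "Chi-square analyses will indicate whether changes on each variable differed significantly across either or both partners". The Data and Safety Monitoring Plan in section 6 names model classes and refers back to the Data Analysis section.

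**The concern.** In a randomised placebo-controlled study the drug effect is the difference between arms. Here the aim, the hypotheses and the described model all concern change within couples or differences between partners.

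Every couple does Task 1, then takes the spray, then does Task 2. Whatever else changes between the tasks, such as practice, getting used to the laboratory, fatigue or a change of topic, falls on the same contrast as the drug. Testing all couples at the same time of day does not remove drift within a visit. Such an effect could create an apparent benefit or hide a real one, and the documents give neither its size nor its direction.

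The statement in section 4.I makes the gap harder to read charitably, because a before-after analysis is what an uncontrolled design would use.

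**Working it through.** **1. Search for an arm contrast.** The plan states no power calculation or between-arm figure, so there is nothing to reproduce. The check is of the text.

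| Place | Comparison written | Arm contrast? |
|---|---|---|
| Section 1, Aim 1 | Task 1 with Task 2 | No |
| Section 1, Aim 2 | Effects of oxytocin on reactivity; measures listed | None stated |
| 4.G General | Decliners with participants; dropouts with completers | No |
| 4.G Hypothesis 1 | First task with second, after oxytocin | No |
| 4.G Hypothesis 2 | Reactivity to second task after oxytocin; no comparator | No |
| 4.G model | Average change over time points | No treatment or treatment-by-time term |
| 4.G chi-square tests | Between-subjects variance; differences across partners | No |
| Section 6, monitoring plan | Model classes only | No |

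**2. What each contrast estimates.** Let δ be the drug effect and ω the common Task 1 to Task 2 shift, both in SD of the couple-level change score. With 1:1 allocation of 36 couples:

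- Before-after, 18 oxytocin couples: estimates δ + ω, SE √(1/18) = 0.236.
- Before-after, all 36 pooled: estimates δ/2 + ω, SE √(1/36) = 0.167 when δ = 0.
- Between arms, 18 v 18: estimates δ, SE √(2/18) = 0.333.

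**3. Illustration.** From the documents: 36 couples and alpha 0.05. Assumed: two-sided testing, 1:1 allocation by couple, and the values of δ and ω. Rates are significant results in the favourable direction, by noncentral t (for example, noncentrality 0.5 × √18 = 2.12 on 17 df gives 0.516) and by simulation for the pooled test when δ is not zero.

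| δ | ω | 18 oxytocin couples | 36 pooled | Between arms |
|---|---|---|---|---|
| 0 | +0.3 | 22% | 42% | 2.5% |
| 0 | +0.5 | 52% | 83% | 2.5% |
| 0.5 | −0.3 | 12% | 1% | 31% |
| 0.5 | 0 | 52% | 29% | 31% |

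In the third row the expected contrasts are 0.5 − 0.3 = 0.2, then 0.25 − 0.3 = −0.05, and 0.5. Only the between-arm contrast is free of ω.

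**4. Precision of the between-arm contrast.** Two-sample t, two-sided 0.05, 80% power, noncentrality d√(n/2) with n couples per arm:

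- 18 v 18: d ≈ 0.96 SD of the change score. Power is about 14%, 31% and 65% at d = 0.3, 0.5 and 0.8.
- 15 v 15: d ≈ 1.06. Section 6 gives 30 couples in one place.

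Adjusting Task 2 for Task 1, with equal SD at both tasks and Task 1–Task 2 correlation r, the residual SD is √(1 − r²) outcome SD. At 18 v 18 with 33 df:

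| Assumed r | Outcome SD needed for 80% power | Power at 0.5 outcome SD | Unadjusted change score, outcome SD needed: 0.961 × √(2(1 − r)) |
|---|---|---|---|
| 0.3 | 0.92 | 33% | 1.14 |
| 0.5 | 0.83 | 39% | 0.96 |
| 0.7 | 0.69 | 53% | 0.74 |

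Effects in this last table are in outcome SD because the change-score SD itself shrinks as r rises.

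**The case against.** The strongest reply is that the plan is under-specified, not committed to a before-after test. The aims ask for the effects of oxytocin in a blinded, randomised design. Section 4.G presents the level-1 model as a first step and then examines between-subjects variance. In a multilevel analysis, level-2 predictors, where arm would enter, normally follow. It also says "Subsequent analyses will be theory-driven and informed by the primary research questions of this study". This stands as far as it goes: an arm term may well be intended. But room for a term does not supply one, and section 4.I points the other way.

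A second reply is that if section 4.I describes the actual design, the hypotheses match it and no arm contrast is possible. That is fair, and it is why the contradiction must be settled first.

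A third is that the rates above belong to tests the plan does not state and rest on assumed order effects at couple level, whereas the plan models both partners and Hypothesis 2 spans many time points. That also stands; they show the mechanism only. Some pages before section 6 were not available, but section 4.G is present and the monitoring plan points to it, so a contrast written elsewhere is unlikely.

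**Conclusion.** The point holds and must be fixed. As written, no oxytocin-versus-placebo contrast exists for any outcome, and the protocol contradicts itself on whether there is a placebo arm.

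A reader might infer that the investigators have decided to judge oxytocin by a before-after test, or that the trial carries a 52% or 83% false-positive rate. The documents support neither. They leave the drug comparison unwritten and give no order effect, so those rates hold only for ω = +0.5, no drug effect, and 1:1 allocation of 36 couples. What does not depend on those assumptions is that, because the spray always lies between the tasks, the worded contrasts estimate drug plus any shift during the visit.

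**What to change.** 1. **Settle the design first.** Reconcile sections 4.A, 4.E (payment text) and 4.I with section 1, section 4.D and the adverse event definition in section 6.
2. **If the placebo arm is run,** restate Aim 1 and Hypotheses 1 and 2 as oxytocin-minus-placebo differences. Test them in the dyadic multilevel model with a treatment term, for example Task 2 adjusted for Task 1, or treatment-by-task; choose one in advance. Enter arm at the level of assignment and state that level: section 1 speaks of participants being assigned, while Aim 1 (both partners) and section 4.D (couples) suggest the couple. Carry the same contrast into the monitoring plan.
3. **If section 4.I governs,** limit conclusions to uncontrolled change and make no efficacy claim. Adding a control arm would be a design change.

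**Cost.** Under option 2 the change is wording plus a model term on data already planned. The price is precision: the between-arm SE is √2 times that of the before-after contrast in 18 oxytocin couples. The protocol should state the effect it can detect, with its assumptions, and settle the number of couples. Section 4.B gives 36; section 6 gives 30 couples, a total planned enrolment of 40, and a table summing to 72 individuals.

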Following informed consent, couples will complete self-report and interview measures in separate rooms. When finished, couples will be escorted into a room together asked to relax for a 15 minute period in this room to acclimate to their surroundings. Following this relaxation period, finger sensors will be placed and baseline measures of all physiological data will be collected. DHEA and cortisol will be collected at 8 time points in all: baseline, immediately following the first conflict-resolution task, 15 minutes after the first conflict resolution task, immediately prior to the second conflict resolution task, immediately after the second conflict resolution task, and 15, 30, and 60 minutes after the conflict resolution task. Skin temperature, skin conductance, and heart rate will be measured continuously from baseline through the end of the laboratory task. Subjective measures will be administered at baseline, immediately before and after both conflict resolution tasks. Following completion of the first conflict resolution task and its associated post-test measurements, couples will self-administer either oxytocin or placebo spray and 45 minutes later will begin the second conflict resolution task. A timeline for completion of the laboratory tasks is outlined below:

Laboratory Task Timeline

TIME	PROCEDURE	MEASUREMENT
8:00am	Informed consent and questionnaires at Charleston Center	Informed consent; pregnancy test; breathalyzer; UDS; Interview and self-report assessment measures
9:00am	Couple escorted to CTRC; Relaxation period begins	
9:20am	Finger sensors placed; Begin baseline measurement	Neuroendocrine: Salivary cortisol; DHEA Physiological: Skin temperature; skin conductance; heart rate Subjective: craving; distress; mood; feelings toward partner
9:30am	Begin conflict resolution task #1	
9:40am	End conflict resolution task #1	Neuroendocrine: Salivary cortisol; DHEA Physiological: Skin temperature; skin conductance; heart rate Subjective: craving; distress; mood; relationship satisfaction; aggression
9:50am	Oxytocin or placebo self-administered	
10:30am	Finger sensors replaced; Begin second baseline measurement	Neuroendocrine: Salivary cortisol; DHEA Physiological: Skin temperature; skin conductance; heart rate Subjective: craving; distress; mood; feelings toward partner
10:40am	Begin conflict resolution task #2	

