10:50am	End conflict resolution task #2	Neuroendocrine: Salivary cortisol; DHEA Physiological: Skin temperature; skin conductance; heart rate Subjective: craving; distress; mood; feelings toward partner
11:05am	15-minute post task assessment	Neuroendocrine: Salivary cortisol; DHEA Physiological: Skin temperature; skin conductance; heart rate Subjective: craving; distress; mood; feelings toward partner

11:20am	30-minute post task assessment	Neuroendocrine: Salivary cortisol; DHEA Physiological: Skin temperature; skin conductance; heart rate Subjective: craving; distress; mood; feelings toward partner
11:50am	60-minute post task assessment	Neuroendocrine: Salivary cortisol; DHEA Physiological: Skin temperature; skin conductance; heart rate Subjective: craving; distress; mood; feelings toward partner

Oxytocin administration and Neuroendocrine Assays

A 40-IU dose of intranasal oxytocin will be self-administered. [name] will provide prescriptions for oxytocin for research participants assigned to the oxytocin condition to research pharmacy services on the MUSC campus, who will compound the oxytocin doses and inform investigators as to the proper number of nasal sprays necessary to achieve the intended dose.

Unstimulated salivary samples will be collected at the previously noted time points by CTRC medical staff to measure cortisol and DHEA. Passive drool will be collected in polypropylene vials and iced immediately. Samples will be aliquoted into 1.81.8 nunc tubes and frozen at -70°C until assayed. Samples will be assayed twice using a high sensitivity salivary cortisol enzyme immunoassay system with an intra-assay precision (coefficient of variation, CV) of 3.35% - 3.65% with a sensitivity of <0.003 ug/dL (Salimetrics LLC). Samples will be analyzed using a PowerWave HT Microplate Spectrophotometer in conjunction with a Precision Series Automated Liquid Handling System (BioTek Instruments, Inc.).

E. Compensation

Participants will be remunerated for their time in cash. Each participant will be paid \$100 upon completion of the study. In the event that participants complete only part of the study, they will be remunerated \$15 for completing self-report and interview measures, \$15 for the first conflict resolution task, and \$70 for taking the oxytocin dose and completing the second conflict resolution task.

F. Maximizing Engagement and Retention

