The experienced research staff conducting this study will make every possible effort to maintain the safety of our research participants, to minimize the risks and burden they incur as a result of participation, and to maximize potential benefits. The knowledge we may gain from the proposed study will address a crucial need for studies to develop and evaluate treatments to improve the health of couples. In the event that new information regarding the risk to benefit ratio becomes available during the course of the study, research participants will be notified. Further, the PI and her mentor will consult with our research team and DSMB to make any necessary study modifications.

Data and Safety Monitoring Plan

This section is based on the recommendations in NIDA's "Guidelines for Developing a Data and Safety Monitoring Plan" (www.drugabuse.gov/funding/dsmb.html).

Summary of the Protocol. The proposed study aims to develop and conduct initial feasibility and efficacy testing of oxytocin for the improvement of couples' conflict resolution skills. The primary outcome in this study includes an improvement in conflict resolution skills and a reduction in subjective, physiological, and neuroendocrine reactivity to dyadic conflict.

Trial Management. The study will be managed from the Division of Clinical Neuroscience within the Department of Psychiatry and Behavioral Sciences at the Medical University of South Carolina.

Data Management and Analysis. A data analytic plan is outlined in the Data Analysis section. Because this study is a preliminary test of a new medication, we are interested in examining a broad range of outcome variables. The main outcome variables include the frequency and severity of negative conflict resolution skills and the frequency and intensity of positive conflict resolution skills as well as

subjective, physiological, and neuroendocrine reactivity to dyadic conflict. Outcome data will be analyzed using regression analyses, structural equation modeling, and hierarchical linear modeling. The alpha level for statistical significance will be set at .05.

Quality Assurance. Data quality will be monitored by random inspection of completed assessment forms by research staff. Any problems with the assessment process, data collection, or data entry will be discussed with the PI and [name].

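### Aim 1: the plan targets Task 1-to-Task 2 change and does not say how the pre-dose Task 1 score enters an arm contrast; if the placebo arm stands, pre-specified adjustment usually adds precision

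*Combined protocol and SAP*

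**What the plan says.** **Target.** Section 1 (Specific Aim 1) states "Conflict resolution skills will be coded according to a well-established system and compared from Task 1 to Task 2". Hypothesis 1 in section 4.G has the same target: "Couples will demonstrate improved conflict resolution skills from the first observational conflict resolution task to the second following the administration of oxytocin".

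**Model.** Section 4.G names linear regression, structural equation and hierarchical linear models. The only modelling detail is a level-1 equation, of which it says "This approach will allow us to examine the average estimates of change in each of the outcome variables over the multiple time points assessed". No arm term or arm-by-time term is written. The Data and Safety Monitoring Plan repeats the model list: "Outcome data will be analyzed using regression analyses, structural equation modeling, and hierarchical linear modeling".

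**Covariates.** The one stated rule, also in 4.G, is "Demographic variables with significant bivariate associations with main outcome variables will be employed as covariates in subsequent analyses". The Task 1 score is not a demographic variable.

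**Timing.** Under Data Collection Procedures, after Task 1 and its measurements, "couples will self-administer either oxytocin or placebo spray and 45 minutes later will begin the second conflict resolution task". Task 1 is therefore measured before dosing.

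**Arms.** Section 1 states "Participants will be randomly assigned to self-administer either a 40 IU dose of intranasal oxytocin or placebo", and the oxytocin administration paragraph speaks of "prescriptions for oxytocin for research participants assigned to the oxytocin condition". Section 4.A, however, describes oxytocin for both partners with no mention of placebo, and section 4.I lists the lack of a control group as a limitation.

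**Size.** Sections 1 and 4.B give 36 couples. Section 6 gives 30 couples, then a planned total of 40 with no unit, above a table that sums to 72 individuals.

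**The concern.** If there are two randomised arms, the effect of oxytocin on skills is a between-arm contrast. The plan's wording leads most naturally to comparing Task 1-to-Task 2 change between arms. A change score carries the noise of both tasks. Using Task 1 as a baseline removes part of that noise unless the two tasks correlate very highly. With 15 to 18 couples per arm and no power calculation in the documents, that precision matters.

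The open choice also matters in its own right. Section 4.D allows ten speaking-turn codes plus optional positive and negative proportions, and 4.G names three model families. Leaving change versus adjusted open adds one more decision that could be made after the data are seen.

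The planned multilevel model does not settle it. With Task 1 means free in each arm and complete data, its arm-by-time term is the change-score contrast. With Task 1 means constrained equal across arms, it is essentially the baseline-adjusted contrast. Both fit the text.

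**Working it through.** The plan states no effect size, SD, correlation, power or sample-size derivation, so there is no figure of its own to reproduce.

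**From the documents:** 36 or 30 couples; significance level 0.05; Task 1 before dosing.

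**Assumed:** 1:1 allocation; both partners of a couple on the same spray (Aim 1 and Data Collection Procedures point this way, although section 1 says participants are randomised); equal SDs at the two tasks; two-sided testing; couple-level Task 1-Task 2 correlation r of 0.3, 0.5, 0.7 and 0.9.

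**Variances of the arm contrast**, in units of the couple-score variance, with N couples in total:

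- Change score: 2(1 − r).
- Adjusted for Task 1: (1 − r²)k, where k = 1 + 1/(N − 4) is the average cost of estimating one slope. For N = 36, k = 1 + 1/32 = 1.031; for N = 30, k = 1 + 1/26 = 1.038.
- Ratio, adjusted to change: (1 − r²)k / [2(1 − r)] = (1 + r)k/2.
- Break-even: r = 2/k − 1.

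Example, N = 36 and r = 0.5: 1.5 × 1.031/2 = 0.77. The change-score analysis would need 1/0.773 − 1 = 29% more couples to match.

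**Detectable difference** (80% power, noncentral t): the standardised value at 18 v 18 is 0.961 on 34 df for change and 0.962 on 33 df for adjusted. At 15 v 15 it is 1.060 on 28 df and 1.061 on 27 df. Each is multiplied by the square root of its variance above. Example, 18 v 18 and r = 0.5: 0.961 × √1.000 = 0.96 and 0.962 × √0.773 = 0.85.

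| Couples per arm | r | Variance ratio | Equivalent extra couples | Detectable difference in SD, change v adjusted |
|---|---|---|---|---|
| 18 | 0.3 | 0.67 | 49% | 1.14 v 0.93 |
| 18 | 0.5 | 0.77 | 29% | 0.96 v 0.85 |
| 18 | 0.7 | 0.88 | 14% | 0.74 v 0.70 |
| 18 | 0.9 | 0.98 | 2% | 0.43 v 0.43 |
| 15 | 0.3 | 0.68 | 48% | 1.25 v 1.03 |
| 15 | 0.5 | 0.78 | 28% | 1.06 v 0.94 |
| 15 | 0.7 | 0.88 | 13% | 0.82 v 0.77 |
| 15 | 0.9 | 0.99 | 1% | 0.47 v 0.47 |

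**Break-even r:** 2/1.031 − 1 = 0.94 at 18 v 18 and 2/1.038 − 1 = 0.93 at 15 v 15. If each partner's Task 1 score has its own slope, k = 1 + 2/(N − 5), which is 1.065 or 1.080, and break-even falls to 0.88 or 0.85.

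**Validity check.** In simulation with 36 couples (4,000 runs per setting, r from 0.3 to 0.8), type I error was 0.046 to 0.058 across the change and adjusted analyses. Both are valid under randomisation; they differ in precision.

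**Which Task 1 score.** Simulated at 18 v 18 with partner correlation 0.5, variance ratios to the change score for the couple mean and for one pooled slope on each partner's own score:

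| Own / cross-partner task correlation | Couple mean | Pooled own-score slope |
|---|---|---|
| 0.5 / 0.25 | 0.76 | 0.75 |
| 0.5 / 0.4 | 0.83 | 0.85 |
| 0.6 / 0.5 | 0.90 | 0.95 |
| 0.7 / 0.6 | 0.96 | 1.02 |

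Neither is better throughout.

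**The case against.** **The point may be moot.** Hypothesis 1 as worded is a pre-post test, section 4.I reports no control group, and the larger gap is that no arm contrast exists at all. This stands. Without a placebo arm there is nothing to gain here, so reconciliation comes first.

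**The comparator is assumed.** A reader might infer that the plan commits to change scores or rules out adjustment. The documents do not support that. They aim at change and name model families that could carry Task 1 in several ways, with biostatistical consultation provided for. The ratios above are therefore gains over the most natural reading of the text, not over a stated analysis.

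**Change scores are not wrong.** A reader might also infer bias. Under randomisation the change-score contrast is unbiased too. The gain is efficiency only, is small at high r, and matters less in a study described as preliminary.

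**Choice of baseline term.** It is tempting to advise against a single pooled own-score slope because it loses the gain in some settings. That does not hold generally. It slightly beats the couple mean at 0.5/0.25, and its one complete loss in the table (1.02) assumes a cross-partner, cross-task correlation (0.6) above the same-task partner correlation (0.5). The documents give none of these correlations.

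**Unstated assumptions.** The allocation ratio is not given. If the planned total of 40 means individuals, there would be about 10 couples per arm; then k = 1 + 1/16 = 1.0625 and break-even is 2/1.0625 − 1 = 0.88. The direction is unchanged below that value.

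**Conclusion.** The point holds as a low-cost improvement to consider, conditional on the placebo arm. The plan targets change, writes no arm term, and has a covariate rule that cannot admit the one baseline measure of the outcome. With 18 couples per arm, adjustment would cut the variance of the arm contrast by about 33%, 23%, 12% and 2% at r of 0.3, 0.5, 0.7 and 0.9. Above r of about 0.94 (0.93 with 15 per arm) it gives no gain and a slight loss. These figures rest on an assumed r, 1:1 allocation by couple, equal SDs and a linear relation between tasks. The omission is one of specification and precision; it does not make the planned analysis invalid. Confidence is medium, because both the existence of a control arm and the size of r are unknown.

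**What to change.** 1. Reconcile the arm statements (sections 1 and 4.D against 4.A and 4.I) and the enrolment figures (36 couples, 30 couples, 40). State the unit of randomisation and the allocation ratio.
2. If the placebo arm stands, write into 4.G, for each skills score, one of two arm contrasts:
   - Task 2 regressed on arm, sex and Task 1 score, with the couple mean as a simple default and partner non-independence modelled (couple random intercept or unstructured partner covariance); or
   - the planned multilevel model with both tasks as outcomes and Task 1 means constrained equal across arms.
3. Fix the choice before unblinding and exempt the Task 1 term from the significance screen for covariates.
4. Because 4.G allows log transformation or a non-parametric fallback, put both tasks on the same scale and say what replaces the adjusted contrast if the fallback is used.

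**Cost:** wording only, since Task 1 is already recorded and coded. One couple-level degree of freedom is spent, or two if each partner's Task 1 score has its own slope, with a small precision loss if r exceeds the break-even.
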